RESEARCH PROTOCOL

1. Particulars of Researcher

Full Name: [name]

Title: Dr

Present Position: Postgraduate Medical Officer

Department: Obstetric & Gynaecology

Office contact number: - Tel: -

[contact]

Email: [contact]

Research expertise (List up to 5 fields of expertise): Gynaecology, Obstetric

2. List of Co-researchers (Include all who have participated in the drafting of this proposal)

 Name: [name] [name] Department: Obstetric & Gynaecology Email: [contact]

2. Name: **[name] [name]**Department: Obstetric & Gynaecology

Email: [contact]

3. Research Proposal

TITLE OF RESEARCH PROPOSAL

A Novel Transcutaneous Electrical Nerve Stimulation (TENS) Device in Patients Post Gynaecology Surgeries: A Triple-Blind, Placebo-Controlled Counterbalanced Crossover Trial

KEY WORDS

Novel transcutaneous electrical nerve stimulation (TENS) device Gynaecology Surgeries

BACKGROUND/ JUSTIFICATION

Recent advances in pain management suggest that the optimal treatment requires interfering with multiple targets on pain pathways, known as multimodal analgesia. This approach utilizes a combination of interventions, each working on a different mechanism of pain to reach maximal pain relief using the lowest effective doses of medications. In addition to medication therapy, there are adjunctive physical and behavioral techniques such as massage therapy, physical therapy, and transcutaneous electrical nerve stimulation (TENS) therapy. According to a study by Baldini G et al, using both pharmacologic and non-pharmacologic interventions can improve pain control, enhance recovery, and increase patient satisfaction. Based on another study by Johnson MI, TENS can be used as an effective adjunct for managing postsurgical pain and to minimize the need for opioid and non-opioid analgesics as part of a multimodal approach to pain.

While the basic premise of TENS has remained relatively consistent, advancements in the device technology have led to more sophisticated devices that can target different nerve pathways, offering potential for more effective pain relief. The evidence for the use of these novel TENS devices in controlling pain is still evolving. This study aims to evaluate the analgesic efficacy and patient acceptability of a novel TENS device in the post-operative period.

OBJECTIVES/OUTCOMES

To evaluate the impact of a novel TENS device on short term pain score during movement at day 1 post gynaecology surgery through a counterbalanced crossover trial: immediately, 1,2 and 4 hours after novel TENS application using a 0-10 Numerical Rating Scale (11 point NRS).

Primary outcome:

Pain score on movement immediately, 1, 2 and 4 hours (a total of 4 measures) after application of active-TENS vs sham-TENS sessions using 0-10 numerical rating scale (11 points NRS): higher score indicates greater pain.

Secondary outcomes:

- Repeated measures of the variance analysis for the serial pain scores across active-TENS vs sham-TENS sessions
- 2. Comparison of pain score on movement- immediately, 1, 2 and 4 hours after application of intervention or sham control sessions of 15 minutes after the first session only (across randomised arms).
- 3. Repeated measures of the variance analysis of the serial pain scores on movement (across randomised arms).
- 4. Identical analyses for similarly recorded blood pressure and pulse- immediately, 1, 2 and 4 hours after active-TENS vs sham-TENS sessions
- 5. Satisfaction score with the intervention immediately after the sessions, using 11 points NRS (higher score greater satisfaction)
- 6. Opioid consumption after application of active-TENS vs sham-TENS device

METHODOLOGY

Study design

This study will employ a randomized, triple-blind, placebo-controlled counterbalanced crossover trial design with 4 hours wash out period. This design allows each participant to serve as their own control, enhancing the reliability of the results as there is no control inter-subject variability at the same time minimising recruitment and outcome ascertainment bias.

Duration

18 months

Setting

Tertiary University Hospital, Gynaecology ward

Participants

The study population will consist of eligible and consented adult women at Day 1 post gynaecological surgery.

Inclusion criteria:

- Age ≥ 18 years old
- Patients undergoing elective or emergency gynaecology surgery (eg: myomectomy, hysterectomy, ovarian/ tubal surgeries) via transverse suprapubic incision under general anaesthesia
- Able to communicate in English or Malay
- Able to provide informed consent

Exclusion criteria:

- Contraindications to TENS (pacemaker, skin lesions)
- Chronic pain on regular opioids

Sample size

- Using Power and Sample Size program, assuming a one-point difference in the 11 points-NRS pain score at each of the four assessment points of immediately after, 1, 2, and 4 hours to be clinically relevant, pain score standard deviation is uniformly at 2.5 at all assessment points, alpha 0.0125(Bonferroni correction for 4 primary outcomes) and power of 95%.
- We will need to study 110 pairs of results. Hence we intend to recruit 110 participants, each participant providing a pair of pain scores at each assessment point following crossover.
- The Bonferroni correction to the p value and the 95% power is statistically conservative, intended to reduce both Type 1 and 2 errors.

Randomization

- -Randomization will be performed using computerized sequence generator.
- -The sequence will be generated in random blocks of 4 or 8 (1:1 ratio) via https://www.sealedenvelope.com/simple-randomiser/v1/lists by a co-investigator not involved in the trial recruitment.
- -Participants will be assigned to one of two trial arms by opening a numbered, sealed, opaque envelope, with the lowest numbered envelope available assigned to the latest recruit.

ARM 1 : TENS followed by SHAM-CONTROL after a 4 hour gap

Or

ARM 2: SHAM-CONTROL followed by TENS after a 4 hour gap

Blinding

- Participants
- **Providers** administering the TENS or sham-controlled treatment first
- Assessors who will evaluate outcomes and collect the feedbacks

To minimize bias and control for placebo effect, a triple-blind design will be employed: 3rd person who is not the provider nor the assessor will control the frequency to be delivered.

TENS device

The Remedius ExStim Pro will be used to deliver external non-invasive stimulation through the Integrated Duo Stimulating Wand. The intervention will be administered by provider after undergoing training on device application by the investigator.

A sham-shock with frequency of 100Hz with amplitude 5mA will be delivered for 30s at the subumbilical region at the start of each session to further enhance the sham and blinding process. The TENS intervention will be delivered as follows:

TENS Parameters

Frequency: 100 Hz
 Pulse width: Medium
 Amplitude: 5 mA

4. **Duration**: Two TENS devices will be used simultaneously, each targeting one site at a time. Each site will be treated for 5 minutes, with two sites treated simultaneously. This will be repeated for 3 rounds, ensuring all 6 application sites are covered, requiring a total duration of 15 minutes per session.

Timing of Intervention:

The TENS intervention will be initiated on Day 1 (morning after) post gynaecology surgeries.

Intervention protocol

TENS First: Participants will receive TENS therapy at a frequency of 100 Hz and 5 mA intensity (set at medium pulse width). The TENS device will be applied at 6 fixed points for 5 minutes each, 1-2 cm lateral to wound edge and 1-2 cm above along, covering the transverse suprapubic incision. After 4 hours wash out, the same TENS device will be used in exactly the same manner with output at sham setting 0 Hz and 0 mA intensity.

[figure not shown]
Control(Sham) First: Participants will receive sham-control TENS therapy with output setting 0 Hz and 0 mA intensity. The TENS device will be applied at 6 fixed points for 5 minutes each, 1-2 cm

VERSION NO:1 VERSION DATE: 15th July 2025

lateral to wound edge and 1-2 cm above along, covering the transverse suprapubic incision. After 4 hours wash out, participants will receive TENS therapy at a frequency of 100 Hz and 5 mA intensity (set at medium pulse width).

[figure not shown]
At the start of both sessions, TENS at a frequency of 100 Hz and 5 mA intensity will be delivered to the subumbilical region, briefly for 30 seconds only to generate a TENS sensation and enhance the sham. If the sensation cannot be tolerated, participation will be stopped.

Participants will still receive standard of care analgesics post gynaecology surgery while undergoing

-the devices will be given by provider who are trained by the investigator (they will undergo training on device application and trial process

Prong application points

Data Analysis:

- Data will be entered into SPSS(Version 27, IBM, SPSS Statistics)
- T-test will be used to analyse mean for normally distributed data
- Mann-Whitney U test for non-normally distributed or ordinal data
- Chi-square test (with Fisher exact test if ≥20% of evaluated have expected cell size number
 5) for categorical data
- Analysis will be on intention-to-treat basis
- Two-sided p-values were reported and p<0.0125 regarded as significant for four primary outcome and p < 0.05 for all other analyses

RESEARCH DATA

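### No pain score is named before session 1, so the carryover-free first-session comparison is valid but less precise than it need be, and return to the starting level cannot be checked

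*Protocol*

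**What the plan says.** Under Objectives/Outcomes, the primary outcome is "Pain score on movement immediately, 1, 2 and 4 hours (a total of 4 measures) after application of active-TENS vs sham-TENS sessions". The objective, secondary outcome 2 and the Sample size section use the same four times, and blood pressure and pulse follow them. No score before either session is named in the text available.

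Secondary outcome 2 compares the arms on scores following "sessions of 15 minutes after the first session only (across randomised arms"). Secondary outcome 3 is the repeated-measures analysis of the serial scores across the same arms.

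The Sample size section sizes the trial on pairs: "assuming a one-point difference in the 11 points-NRS pain score at each of the four assessment points", "pain score standard deviation is uniformly at 2.5 at all assessment points", and "alpha 0.0125(Bonferroni correction for 4 primary outcomes) and power of 95" per cent, leading to "We will need to study 110 pairs of results. Hence we intend to recruit 110 participants". No power is stated for the first-session comparison. Under Randomization, "The sequence will be generated in random blocks of 4 or 8 (1:1 ratio"), so about 55 women per arm.

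Under Data Analysis, the tests listed for scores are the t-test and Mann-Whitney U, neither of which takes a covariate. The significance rule is "Two-sided p-values were reported and p<0.0125 regarded as significant for four primary outcome and p < 0.05 for all other analyses".

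**The concern.** The two sessions are four hours apart, so an effect of active TENS in session 1 could still be present in session 2. The first-session comparison cannot be affected by this. It is also made before a woman has felt both active and zero output at the wound. The protocol does not give the comparison this role in words, but the design gives it that role.

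In this comparison a woman is not her own control. Eligibility covers elective and emergency operations of several kinds, so starting pain is likely to differ between women, and that variation enters the error term in full. A score taken before session 1 would remove part of it.

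The same missing score limits the check on washout. The session-1 4-hour score shows where pain stands at about the start of session 2, but there is no session-1 starting value to set beside it.

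A later SAP can add a covariate. It cannot supply a score that was never taken.

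**Working it through.** **Inputs.** From the protocol: difference 1 point; SD 2.5; primary alpha 0.0125 two-sided with 95% power; alpha 0.05 two-sided for other analyses; 110 women allocated 1:1, so 55 per arm. Assumed, because the protocol does not give them: the correlation r between a pre-session score and a later score, the within-woman correlation ρ between paired scores, and the correlation c between time points within a session.

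**1. The protocol's own figure.** Paired comparison: n = [SD × (z for 1 − α/2 + z for power) / difference]² = [2.5 × (2.498 + 1.645) / 1]² = 107.3, so 108. By the noncentral t, 111 are needed and 110 pairs give 94.9% power. The stated 110 reproduces, with 2.5 used as the SD of the paired difference. It is worded as the SD of the score. The two are equal when ρ = 0.5, because SD of difference = score SD × √[2(1 − ρ)].

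**2. Secondary outcome 2, one time point, unadjusted.** Standard error = 2.5 × √(2/55) = 0.477. Noncentrality = 1/0.477 = 2.10 on 108 degrees of freedom. Power at alpha 0.05 is 54.7%. The difference detectable with 80% power is 0.477 × (1.960 + 0.842) = 1.34 points. For 80% power at 1 point, the normal approximation gives 99 per arm.

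**3. The same, adjusted for a pre-session score.** Residual SD = 2.5 × √(1 − r²).

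| Assumed r | Residual SD | Power, 55 per arm |
|---|---|---|
| none (unadjusted) | 2.50 | 55% |
| 0.3 | 2.38 | 59% |
| 0.5 | 2.17 | 67% |
| 0.6 | 2.00 | 74% |
| 0.7 | 1.79 | 83% |

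Reaching 80% with 55 per arm needs r of about 0.66 to 0.67. At r = 0.5, 80% power needs 74 per arm instead of 99, because the variance falls by a factor of 1 − 0.25 = 0.75.

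**4. If 2.5 is the SD of the paired difference.** Score SD = 2.5 / √[2(1 − ρ)].

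| Assumed ρ | Score SD | Unadjusted power | Adjusted, r = 0.5 |
|---|---|---|---|
| 0 | 1.77 | 84% | 92% |
| 0.3 | 2.11 | 69% | 81% |
| 0.5 | 2.50 | 55% | 67% |
| 0.7 | 3.23 | 36% | 46% |

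Adjustment helps in every row.

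**5. Secondary outcome 3, unadjusted.** The arm effect in a repeated-measures analysis rests on the mean of four scores, with SD = 2.5 × √[(1 + 3c)/4]. With a 1-point difference at all four times:

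| Assumed c | SD of the mean | Power, 55 per arm |
|---|---|---|
| 0.4 | 1.85 | 80% |
| 0.5 | 1.98 | 75% |
| 0.6 | 2.09 | 70% |
| 0.7 | 2.20 | 66% |

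Baseline adjustment also reduces this variance. If the pre-session score correlates 0.5 with each later score, 2.5² × [(1 + 3c)/4 − 0.25] at c = 0.7 gives SD 1.81 and power 82%, against 66% unadjusted.

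**6. Chance imbalance.** If the pre-session SD is also 2.5 (assumed), the arm difference in starting pain has standard error 0.477. By the normal distribution, an imbalance of 0.5 point or more in either direction occurs in about 29% of trials. Without the score it can be neither seen nor allowed for in the estimate.

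**The case against.** The case on the other side is substantial, and most of it limits the point.

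- **Validity.** The primary comparison is within-woman and needs no baseline. The first-session contrast is randomised, and its standard error already allows for chance imbalance. A reader might infer that imbalance in starting pain biases the comparison. It does not; the loss is precision. This stands.
- **Cause of the low power.** A reader might blame the missing baseline for the 55%. It comes mainly from having 55 per arm in a trial sized on 110 pairs. A secondary outcome for which no power is claimed is not an error for falling below 80%. This stands.
- **Scope of the gap.** A reader might infer that neither session has a start score. The session-1 4-hour score falls at about the start of session 2 and can serve there. Only session 1 lacks one.
- **Scope of the 55%.** It applies to one time point and depends on how the SD is read. It does not describe outcome 3, which has about 66% to 80% unadjusted.
- **Documents not shown.** Covariate adjustment is commonly left to an SAP, and the count of four measures concerns the outcome and does not say that nothing else is recorded. A case form may hold a pre-session score. This stands as a caveat, and the fix allows for it. It does not remove the point, because the times at which pain is to be scored are set in the protocol and no time before session 1 is among them.

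**Conclusion.** The point holds as a precision issue in secondary analyses. The protocol names pain scores only after application and none before session 1. The one pain comparison free of carryover is therefore less precise than it could cheaply be, and return to the starting level before session 2 cannot be checked.

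On the protocol's wording of the SD, a single-time-point first-session comparison gains roughly 12 to 28 percentage points of power from adjustment (55% to 67–83%) at baseline correlations of 0.5 to 0.7. Those correlations are assumptions. The starting figure itself depends on whether 2.5 is the SD of the score or of the paired difference. Outcome 3 starts higher and gains as well. Nothing here calls the primary analysis into question.

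**What to change.** Record one pain-on-movement score on the same 0–10 scale just before the 30-second stimulation that opens session 1. Use the session-1 4-hour score as the starting value for session 2. State that secondary outcomes 2 and 3 are analysed by ANCOVA or a mixed model adjusted for the pre-session-1 score. If the case form already holds such a score, only the adjustment has to be added.

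The cost is one extra movement-evoked rating per woman and a sentence or two of analysis wording. The sample size and the session schedule do not change. The rating has to be in place before recruitment to be of use, since it cannot be recovered for women already treated.

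### The active-versus-sham analyses name no period term in a two-sequence crossover; a shift between sessions would cost power, little up to 1 point and materially from about 1.5 points

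*Protocol*

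**What the plan says.** The Randomization section sets up two arms in a 1:1 ratio, with blocks of 4 or 8: TENS then sham, or sham then TENS, separated by 4 hours. Timing of Intervention fixes the first session: "The TENS intervention will be initiated on Day 1 (morning after) post gynaecology surgeries". The Intervention protocol says that usual postoperative analgesia continues.

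The primary outcome is pain on movement after active versus sham sessions at four time points. The Data Analysis section states "T-test will be used to analyse mean for normally distributed data", gives Mann-Whitney U for other continuous or ordinal data, and adds "Two-sided p-values were reported and p<0.0125 regarded as significant for four primary outcome". Secondary outcome 1 is "Repeated measures of the variance analysis for the serial pain scores across active-TENS vs sham-TENS sessions". Secondary outcomes 2 and 3 compare the randomised arms, and item 2 is restricted to the first session.

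The Sample size section works from "assuming a one-point difference in the 11 points-NRS pain score at each of the four assessment points", "pain score standard deviation is uniformly at 2.5 at all assessment points" and "alpha 0.0125(Bonferroni correction for 4 primary outcomes) and power of 95" per cent, and concludes "We will need to study 110 pairs of results".

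No section names a period or sequence term.

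**The concern.** Every woman has her second session later in her recovery than her first, after more analgesia. If pain on movement differs between the two occasions for reasons unrelated to TENS, that shift adds to the sham-minus-active difference in one arm and subtracts from it in the other. A comparison that pools the arms by session type counts this known, opposite-signed shift as random scatter. Randomising to two sequences lets the analysis remove it, and the active-versus-sham tests named in the protocol do not.

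The main stake is power at the four primary time points. A second stake arises if the arms end with unequal numbers of complete pairs. The cancellation between arms is then incomplete and part of the shift remains in the estimate.

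**Working it through.** **Inputs from the protocol.** Difference δ = 1 point; SD 2.5; two-sided alpha 0.0125; power 95%; 110 pairs; 1:1 allocation, so 55 per sequence.

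**Inputs assumed.** The period shift p, because the protocol gives none; values of 0.5 to 2 points are shown. Complete pairs of 45 versus 55 for the unbalanced case. The SD of 2.5 is taken as the SD of the within-woman difference, because only that reading reproduces 110.

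**Step 1: the protocol's own figure.** For a paired two-sided test, n = (SD × (z₁₋α/₂ + z_power) / δ)² = (2.5 × (2.498 + 1.645))² = 107.3. Using t quantiles and iterating gives 110.2. The exact power at 110 pairs is 94.9%. The figure of 110 is reproduced as a simple paired t-test with no period term.

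**Step 2: what the shift does.** Let p be the fall in pain from session 1 to session 2 that is due to time alone. The sham-minus-active difference centres on δ − p in Arm 1 (TENS first) and on δ + p in Arm 2.

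- Mean with 55/55: (55(δ − p) + 55(δ + p)) / 110 = δ, so there is no bias.
- True standard error of the mean: 2.5/√110 = 0.238, unaffected by p.
- Standard error that the unadjusted test estimates: about √((6.25 + p²)/110).

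The loss comes only from this overestimated standard error. With a critical value of about 2.54 (109 df), power is approximately Φ((1 − 2.54 × √((6.25 + p²)/110)) / 0.238). At p = 1 this is Φ((1 − 2.54 × 0.2567)/0.238) = Φ(1.46), about 92.8%. Simulation with fixed 55/55 sequences gives:

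| Assumed shift p | Rise in error variance (p²/6.25) | Power, unadjusted | Power, period-adjusted |
|---|---|---|---|
| 0.5 | 4% | about 94.5% | about 95% |
| 1.0 | 16% | about 92.6% | about 95% |
| 1.5 | 36% | about 88.8% | about 95% |
| 2.0 | 64% | about 82.2% | about 95% |

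Repeat simulations differ by a few tenths of a percentage point.

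**Step 3: type I error, balanced.** With no treatment effect and p = 1, the unadjusted test rejects in about 0.7% of simulated trials against the nominal 1.25%. It is conservative.

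**Step 4: unequal complete pairs.** With 55 complete pairs in Arm 1 and 45 in Arm 2, the mean is (55(δ − p) + 45(δ + p))/100 = δ − 0.1p. At p = 1 the expected estimate is 0.9. The true standard error is 2.5/√100 = 0.25; the estimated one is about √((6.25 + 0.99)/100) = 0.269; the critical value is about 2.544. Power is then about Φ((0.9 − 2.544 × 0.269)/0.25) = Φ(0.86), about 80%. Simulation also gives about 80% unadjusted, against about 92% with period adjustment. The adjusted figure is below 95% mainly because only 100 pairs remain. With the imbalance reversed, the bias would favour TENS.

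**The case against.** **The shift is not documented.** This stands. The protocol gives the timing and the continuing analgesia, and nothing on how pain moves between sessions. Analgesia might hold scores level. A reader might infer that pain is known to change, but it is only plausible, and the size is an assumption throughout.

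**Larger losses.** A reader might put √(6.25 + p²) into a power formula as the SD and obtain 91%, 85% and 77% at shifts of 1, 1.5 and 2 points. That treats a fixed, balanced shift as if it made the mean itself more variable. Allocation is 1:1, so the mean is unaffected and the loss is smaller, as tabulated.

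**Validity.** A reader might infer a biased or falsely positive primary result. With balanced sequences there is no bias and the test is conservative. Bias needs unequal complete pairs, and the protocol gives no dropout figure. At 55 versus 50 and a 1-point shift it would be only 5/105, about 0.05 points.

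**The sequences are used elsewhere.** This stands in part. Secondary outcome 2 is free of any period effect, and so is item 3 if it is confined to the first session. Neither is the primary analysis.

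**A SAP may add the term.** It may. However, the protocol does name its tests, down to the software and the Fisher criterion, and the tests that it names contain no such term.

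**The baseline is itself a reading.** The power figures concern the four primary tests at 0.0125, not secondary outcome 1 at 0.05, and they presuppose a paired test that Data Analysis does not name. Independent-sample tests on 110 versus 110 scores would have about 68% power; that is a separate question. Also, if 2.5 came from crossover differences that already contained a period shift, part of the inflation is already counted.

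**Conclusion.** The point holds as a conditional matter of efficiency. The named active-versus-sham analyses leave out a period term that the two-sequence design makes available. With balanced arms the cost is about 2 percentage points of power at a 1-point shift (94.9% to 92.6%), about 6 at 1.5 points and about 13 at 2 points. If complete pairs end at 45 versus 55 and the resulting bias runs against TENS, power at a 1-point shift is about 80% instead of 92%.

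These figures rest on an assumed shift, on 2.5 being the SD of within-woman differences free of a period shift, and on a paired analysis. They do not support a claim that the planned tests would produce extra false positives in the balanced design. The change is worth making because it costs almost nothing and protects against a shift whose size cannot be known beforehand.

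**What to change.** In Data Analysis, state that each primary time point will be analysed by a linear mixed model with treatment, period and sequence as fixed effects and participant as a random effect. Add period and sequence to the repeated-measures model of active versus sham sessions.

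With complete pairs, this gives the same treatment test as comparing period-1 minus period-2 differences between the arms. With incomplete pairs the two are not the same. The mixed model is then preferable because it keeps women with only one session, in line with the stated intention-to-treat basis.

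The cost is one degree of freedom (109 to 108 with 110 pairs) and analysis wording only. No procedure, visit or sample size changes. The wording should be settled before unblinding, so that the term cannot look data-driven.

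### Secondary outcomes 1, 3 and 4: a mixed model on every recorded score would suit the intention-to-treat basis better than repeated-measures ANOVA, at little cost

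*Protocol*

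**What the plan says.** Under Secondary outcomes, the Protocol names a method for the serial scores, not only an endpoint. Item 1 is "Repeated measures of the variance analysis for the serial pain scores across active-TENS vs sham-TENS sessions". Item 3 is "Repeated measures of the variance analysis of the serial pain scores on movement (across randomised arms"). Item 4 carries the same approach to haemodynamic measures: "Identical analyses for similarly recorded blood pressure and pulse- immediately, 1, 2 and 4 hours after active-TENS vs sham-TENS sessions".

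Each session yields four scores ("Pain score on movement immediately, 1, 2 and 4 hours (a total of 4 measures) after application"), so a woman who completes both sessions has eight.

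The Data Analysis section states "Analysis will be on intention-to-treat basis" without defining the term further. It names the package ("Data will be entered into SPSS(Version 27, IBM, SPSS Statistics") but no procedure, and it does not say how an incomplete series is handled.

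Two other statements bear on completeness:
- Intervention protocol: a brief test stimulation opens both sessions, and "If the sensation cannot be tolerated, participation will be stopped".
- Sample size: 110 pairs are needed, and "Hence we intend to recruit 110 participants, each participant providing a pair of pain scores at each assessment point following crossover". No allowance is made for losses.

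**The concern.** Classical repeated-measures ANOVA needs a full row of scores for each woman. One missed reading removes her and all her other readings. Intention to treat, as usually understood, keeps every randomised woman in the analysis. Run in the ordinary way, the named method therefore analyses a narrower group than the stated basis suggests.

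Incomplete series are foreseeable. A woman may miss a single reading, or may be stopped at the start of session 2 with four valid session-1 scores already recorded.

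Two things are at stake, both in secondary analyses only: precision, if scattered readings are missed, and whether the result describes all women as randomised.

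**Working it through.** **1. The plan's own figure.** Inputs from Sample size and Data Analysis: difference 1 point, SD 2.5, two-sided alpha 0.0125, power 95%. For a paired comparison:

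n = (SD × (z₁₋α/₂ + z_power) / difference)² = (2.5 × (2.498 + 1.645) / 1)² ≈ 107.3, so 108.

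The t-based calculation gives 111, and power at 110 is 94.9%. The stated 110 is reproduced, with 2.5 acting as the SD of the paired difference. All 110 recruited women are needed as pairs.

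**2. Women with a complete series.** The documents give no missingness rate, so the per-score rate m is an assumption. If scores go missing independently, the complete share is (1 − m)^k, with k = 8 for active versus sham and k = 4 for one session. Item 3 does not itself say first session only. The four-score reading takes it together with item 2, which does.

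| m | k = 8: complete of 110 | lost | k = 4: complete of 110 | lost |
|---|---|---|---|---|
| 1% | 101.5 | 7.7% | 105.7 | 3.9% |
| 2% | 93.6 | 14.9% | 101.5 | 7.8% |
| 3% | 86.2 | 21.6% | 97.4 | 11.5% |
| 5% | 73.0 | 33.7% | 89.6 | 18.5% |
| 10% | 47.4 | 57.0% | 72.2 | 34.4% |

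**3. Dependence on independence.** Hold m at 5% with eight scores, but let missingness correlate within women (latent-normal correlation 0.3, 0.5, 0.8). The loss falls from 33.7% to about 27%, 22% and 14%. If missingness is whole-woman dropout at 5%, the loss is 5%.

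**4. Precision of active minus sham, averaged over the four time points.** Assumptions: equal SDs, correlation 0.7 within a session and 0.5 between sessions. With SD 2.5 for a single score (it cancels in the ratio):
- variance of a session mean = 6.25 × (1 + 3 × 0.7)/4 = 4.844
- covariance between the two session means = 6.25 × 0.5 = 3.125
- variance of one woman's difference = 2 × (4.844 − 3.125) = 3.4375
- with 110 complete women: 3.4375/110 = 0.0313; with 73: 3.4375/73 = 0.0471

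A model on all recorded scores loses little from scattered gaps, so its variance stays close to 0.0313. The ratio of completers-only variance to all-scores variance cannot exceed 1/(1 − m)^8, which is 1.08, 1.18, 1.28 and 1.51 at 1%, 2%, 3% and 5%. Comparing completers only with generalised least squares on all scores gives about 1.08, 1.17, 1.27 and 1.50, just under that ceiling.

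**5. The protocol's own stopping rule.** Suppose nothing is missing except session 2 for women stopped at its start. The variance ratio is then about 1.01 with 5% stopped and 1.02 with 10% stopped. A woman without session 2 adds almost nothing to a within-woman contrast, so keeping her barely changes precision. Under a first-session reading of item 3 she has all four scores and is not dropped. A woman stopped at the start of session 1 has no post-session scores, so neither method recovers anything from her.

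**The case against.** The strongest reply is that no contradiction is shown. The protocol names no SPSS procedure, no completers population and no imputation rule, and it leaves intention to treat undefined. In its core sense that term means analysing women in the group to which they were randomised, which repeated-measures ANOVA can respect. The same package also fits mixed models for repeated measures. Handling of incomplete series is ordinary SAP content, and the SAP is not at hand. This stands. A reader might infer that the ANOVA can only use complete series and that the two statements cannot both be followed. The documents do not support that, because it presupposes the classical listwise procedure with no imputation.

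A reader might also infer that up to a third of the women would be discarded. That is not a figure from the protocol and not an upper bound. It needs eight scores, 5% missing per score and independence: clustering gives less, and 10% missing gives 57%. These are inpatients followed over hours on Day 1, so low rates are plausible.

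Nor does the stopping rule drive the precision loss, as step 5 shows. The effect is confined to secondary outcomes. As a rough scale, one paired contrast (1 point, SD 2.5) at the secondary alpha of 0.05 still has about 92% power with 73 women.

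The reply does not remove the point altogether. The protocol does name a method, its ordinary form drops incomplete series, and nothing in the Data Analysis section offsets this.

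**Conclusion.** The point holds as a cheap improvement to secondary outcomes 1, 3 and 4, not as an error that invalidates the plan. The named method, as ordinarily run, fits poorly with the stated analysis basis.

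Its size depends on assumptions that the protocol does not supply. With independently missed scores at 1% to 5%, completers-only analysis of active versus sham gives up about 8% to 50% in variance, given correlations of 0.7 and 0.5. With clustered missingness the loss of women is smaller. With session-2 stopping alone, the precision cost is 1–2% and the argument is about keeping women as randomised.

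The four primary comparisons are made time point by time point and do not use this model. The absence of a recruitment reserve concerns the primary sample size and adds little weight here.

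**What to change.** In secondary outcomes 1 and 3, and in the repeated-measures part of item 4, replace the ANOVA with a likelihood-based linear mixed model (the MIXED procedure in the named package) fitted to every recorded score from every randomised woman:
- **Active versus sham:** fixed effects for treatment, time point, treatment-by-time and period, with a stated within-woman covariance (unstructured, or woman as a random effect).
- **Randomised arms, first session:** fixed effects for arm, time point and arm-by-time on session-1 scores, again with a stated within-woman covariance.

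Say in item 3 whether it is limited to the first session, as item 2 is. Keep the completers-only ANOVA as a sensitivity analysis.

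The cost is a change of wording: same software, no new data, no more participants. The downside is reliance on a missing-at-random assumption and on a covariance structure that must be chosen in advance. Completers-only analysis generally needs a stronger assumption about the missing scores.
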